#### Laboratory Data, Blood Pressure, and Heart Rate

The incidence of hypocalcemia after the first dose of IP will be summarized using descriptive statistics. Hypocalcemia will be defined in two ways, with the subject incidence of corrected serum calcium of < 7.5 mg/dL, **8.0 mg/dL**, and < 8.4 mg/dL both being summarized. Subject incidence of ionized calcium value < **0.94 mmol/L**, < 1.05 mmol/L, and < 1.00 mmol/L will be summarized. Section: Appendix C Pregnancy and Lactation Notification Worksheets Replace:

Footnotes on the Pregnancy and Lactation Notification Worksheets was removed.

Page 38 of 42

Product: Cinacalcet HCI ProtocolNumber. 20140159 Date: 16 March 2016

Page39 ot42

### At.GEN• Pregnancy Notification Wor1<sheet

Fax Completed Form to the Country-respective Safety Fax line

1. Case Administrative Info	rmation			
Protocol/Study Number:				
StudyDesign: Interventional Observational (If Observational: Prospective Retrospective)				
2. Contact Information			:	Site #
Phone {	Fax(	)		=
Addreis				
Subi4KtiOM	Subject Gender	r: O Female O	t.We Subj	eetOOB: mm 1 dd
4_ AmgenProduct Exposu	re			
Amgen Produet	Dose at time of conception	Frequency	Route	Start Date
				mm .J. .,Jtyyy y
W:tS lheen product (or study dru If yes, provide product (or s	0,	D Yes ○ No mm /dd	уууу	
Did the subject withdraw from the	ne study? O Yes	O No		
5_ Pregnancy I formation				
Pregnant female'sLMP mm. Esôm.lted date oi delivery mm	.1			) NIA
If N/A, date of termination (aCl:Ual or planned) mm				
Hasthpregnant female at eady de livered? O Yes O No O Iklk.nown O N/A				
If yes.provide dateof delivery: nvn /dd I YYYY: Was t/'e inbnthealthy? O Yes O No O Uhknown O N IA				
Hany AdYerse Ewntwas experience				

Form Compl eted by:	
Print Harne=,	Trtle:
Signature:	Date:

Amgenmaint in & a Pregnancy Sur,-emanceProgram thai OOI»<U&Ia about pregMnCy Of P Cmenoruve been exposed to an Amgenp-ocluci ruectly or v. a mare&ecUalpartner...omation trom the program arts from other &01.000 % of mronna JOn. WI cootribute to incMitting/ trutulit/iai?)) cd.Rs/necp pa.w.i.l. and ther Cloctor & In the Liture man empire thronneabeur510n& about talk g an Amgen <1.11ng pregNncy.

Effect!\e Date: Mate:h 27, 2011

Page 1 ot 1

Product: Cinacalcet HCI ProtocolNumber: 20140159 Date: 16 March 2016

### Page40 of42

					Print form
	AIIIGEH	" Lactation Noti	ficationWo	orksheet	
Fax Completed Form to the		ve Safety Fax Line ELECT OR TYPE IN		erfax number	
Protocol /Study Number:					
Study Design: $\boldsymbol{O}$ Interventional	$\mathbf 0$ Observational	(ItObservational: $0$	Prospective	O Retrospective)	
Contact Informatron Investigator Name Phone () Institution	Fax I	j		Site# Email	
Address					
3. Subject Information Subject ID #	Subject Date	e of Birth: mm	/ dd/ y	ууу	
4 Amgen Product Exposu	ire				
Amgen Product	Dose at time of breast feeding	Frequency	Route	Start Date	
				mm / dd /yyyy	-
Was the Amgen product (or stu	udy drug) discontinue	ed? O Yes O N	D		
If yes, provide product {or	study drug)stop date	e: rrm /dd	_/уууу		
Did the subject Wthdraw from	the study? $0$ Yes	O No			
5 Breast Feed;ng Inform	tion				
Did the mother breastfeed or provto	le the infant with pun	nped breast mik 'or'llhil	actively takin	ig an Amgen product? Oiyes C	) No
If No, provide stop date: $\ensuremath{rr}$	m /dd	lyyyy			
Infant date of birth: rrrn/d					
Infantgender: O Female O M Is theinfantheatthy? O Yes O		O NIA			
If any Adverse Event v.as experen	ced by the mother or	the infant, provide br	ef details		

Form completed bY:	
PrintName	Title:
Sign ture;	D e

Amgen maintains II Lactation Surveillance Program that collects dillta about wanen who havebeen exposed to an Amgen product whe breastfeeding. Information from this program and from dher sources of information willcontribute to knowledge that ultimately coold help patients: and their doctors in the future make more informeddecisions about king an Amgen medicalioo duringlactation. Effective Date: 03 Apfit 2012, version 2. Page 1011

**AMGEN** 

Product: Cinacalcet HCI ProtocolNumber: 20140159 Date: 16 March 2016

With:

# AIII'I(;Eit" Pregnancy Notification Worksheet

Fax Completed Form to the Country-respective Safety Fax Line SELECTOR TYPE NA FAXH

n. Gase Administrative in	formation			
Protocol/Study Number:				
Study Design: Interventional Observational (If Observational: Prospective Retrospective)				
2. Contact Information				
Investigator Name				Ste#
Phoneli	Fax I	i	Er	mali
Institution				
Address				
		5	B	
Subject D#	Subject Gen	der:DFemale	D Male Subj	ject DOB: mm/ dd/ yyyy
4. Amgen Product Exposur	e			
r. Angen i roudet Exposu				
Amgen Product	Dose at time of conception	Frequency	Route	Start Date
				mm ldd lyyyy
Was the Amgen product (or stu	idy drug) di sconti nu	ed? D Yes D	No	
If yes, provide product (o	rstudydrug)s t opda	ate: mm/dd	tyyyy	
Did the subject withdraw from	the study? D Yes	D No		
5. Pregnancy Information				
Pregnant fem #e 's LMP mm / dd / კუუუ D Unknow n				
Estimated date of delivery mm/dd/yyyyDUnknown DN/A				
	If N/A, date of terminaton (actual or planned) mm/ dd/ yyyy			
	ualor planneu)mm_	/ 44		
If N/A, date of termination (act	elivered? DYes	D No D Unkno	own D N/A	
If N/A, date of termination (act Has the pregnant female already d	elivered? DYes /:mm1dd	D No D Unkno	own D N/A	

Form Completed by:	
Print Name:	Title:
Signature:	Date:

Effective Date: March 27 . 2011

Page 1 of 1

CONFIDENTIAL

Page 41 of 42

**AMGB1** 

Product: Cinacalcet HCI ProtocolNumber: 20140159 Date: 16 March 2016

Page 42 of 42

	Allti(;Et	f Lactation Noti	fication W	orksheet
Fax Completed Form to the		ve Safety Fax Lin ELECT OR TYPEIN		er fax number
1. Case Administrative Inf	ormation			
Protocol/Study Number:				
Study Design: D Inlervenijonal	D Observálbnal	(If Observaiional: D	Prospect ve	DRetrospective)
2. Contact Information				
Investigator Name				Site #
Phone ()	Fax L_	)		Email
Institution				
Address				
3. Subject Information				
Subject ID #	Subject Date	of Birth: mm	/ dd/ y	ууу
4. Amgen Product Exposur	e			
4. Alligen i Toudet Exposul			ú	
AmgenProduct	Dose at time of breast feeding	Frequency	Route	Start Date
				mmtdd/YYYV
Was the Amgen product (or stu	idv drug) d i scontinue	ed? O Yes O N	10	
If yes_provide product (or				
Did the subject IMihdraw from t				
5. Breast Feeding Informa	tion			
			ne acijvely lak	ingan Amgen product? DYes DNo
If No, provide stop date: mr Infant dale of birth:mm /dd				
Infant gender: $\mathbf{O}$ Female $0$ M				
Is theinfanthea thy? O Yes O		n O N/A		
If any Adverse Event was expelien	cedby the mother o	r theiinfant,provide bi	niefdetails.:	
	-			

Fonm Completed by:	
Print Name:	Title:
Signature:	Date:

Effective Date:03Aprill2012,verston2.

Page 1of 1

AMGB1

Product: Cinacalcet HCI Protocol Number: 20140159 Date: 01 June 2016

Page 1 of 2

#### Rationale:

The purpose of the superseding protocol amendment is to correct administrative and typographical changes in Section 10.4.4 Safety Endpoints.

CONFIDENTIAL

Product: Cinacalcet HCI Protocol Number: 20140159 Date: 01 June 2016

**Description of Changes:** 

Section: Global

Replace:

16 March 2016

With:

01 June 2016

Section: Title Page Date

Added:

Superseding 3.1: 01 June 2016

Section: 10.4.4 Safety Endpoints

Replace:

Hypocalcemia will be defined in two ways, with the subject incidence of corrected serum calcium of < 7.5 mg/dL, 8.0 mg/dL, and < 8.4 mg/dL both being summarized. Subject incidence of ionized calcium value < 0.94 mmol/L, < 1.05 mmol/L, and < 1.00 mmol/L will be summarized.

With:

Hypocalcemia will be defined in two ways: with the subject incidence of corrected serum calcium of < 7.5 mg/dL, < 8.0 mg/dL, and < 8.4 mg/dL being summarized; and with subject incidence of ionized calcium value < 0.94 mmol/L, < 1.05 mmol/L, and < 1.00 mmol/L being summarized.

CONFIDENTIAL

Page 2 of 2

---

**AMGEN®**

---

#### Table of Abbreviations

Refer to Study Glossary in the protocol. Additional abbreviations are below:

Abbreviation/Acronym	Definition
25(OH)D	25-hydroxyvitamin D
CDM	Clinical Data Management
CSR	Clinical Study Report
EOI	Events of Interest
IV	Intravenous
QTcB	Corrected QT using Bazett's formula
SAP	Statistical Analysis Plan
IPW	Inverse Probability Weighting

## 1. Introduction

The purpose of this statistical analysis plan (SAP) is to provide details of the statistical analyses that have been outlined within the protocol amendment **3** for cinacalcet Study 20140159 dated **16 March 2016**. The scope of this plan includes the **planned interim and final analyses** that are planned and will be executed by the Biostatistics department unless otherwise specified.

## 2. Objectives

### 2.1 Primary

To characterize the long-term safety and tolerability of cinacalcet in pediatric subjects with chronic kidney disease (CKD) receiving dialysis.

### 2.2 Secondary

To characterize the long-term effect of cinacalcet in pediatric subjects receiving dialysis on laboratory parameters associated with chronic kidney disease – mineral and bone disease (CKD-MBD)

### 2.3 Exploratory

To characterize the long-term effect of cinacalcet in pediatric subjects on linear and pubertal growth.

## 3. Study Overview

### 3.1 Study Design

This is a phase 3, 32-week, multicenter, single-arm, extension study designed to characterize the long-term safety and tolerability of cinacalcet in pediatric subjects.

**Subjects will remain on cinacalcet treatment for 28 weeks after enrollment from parent studies 20110100 or 20130356, or until the time of renal transplant or parathyroidectomy, whichever occurs first. The treatment period is followed by a 4-week safety follow-up period.**

The overall study design is described by a study schema at the end of the protocol synopsis section.

#### 3.1.1 Subjects From Study 20130356

**The screening period for Study 20140159 begins when the informed consent, and assent if applicable, is signed and concludes when the subject is either enrolled into the trial or screen failed. The informed consent can be signed up to 7 days ( $\pm$  3 days) prior to Study 20140159 day 1. Eligible subjects who reach Study 20130356 termination or complete the 20-week treatment period in**

---

Product: Cinacalcet HCl  
Statistical Analysis Plan: 20140159  
Date: 24 May 2016

Page 6 of 36

---

study 20130356, will either continue, restart, or start cinacalcet treatment in this study, depending on their cinacalcet treatment status at the time of enrollment. Eligible subjects will begin procedures in Study 20140159 at the Study 20130356 end of investigational product (EOIP) study visit, and will therefore not complete the safety follow-up period in Study 20130356; ie, the EOIP visit in Study 20130356 and Study Day 1 in Study 20140159 will be the same visit unless there is an administrative delay. Eligible subjects will complete **Study Day 1 of Study 20140159** assessments and confirm eligibility in IVR system prior to dispensing IP on **study day 1**.

Eligible subjects from 20130356 who were randomized to the SOC arm in Study 20130356 will begin cinacalcet treatment on **Study Day 1** in Study 20140159 if their iPTH is  $\geq 300$  pg/mL and cCa is  $\geq 8.8$  mg/dL **during screening in Study 20140159**. Eligible subjects from the cinacalcet arm in 20130356 will continue cinacalcet treatment on **Study Day 1** if their iPTH is  $\geq 150$  pg/mL and cCa is  $\geq 8.4$  mg/dL **during screening in Study 20140159**. **If IP has been withheld or missed for more than 14 days on Study Day 1, the subject will resume dosing at the starting dose level once all restart criteria are met.**

All subjects from 20130356 will be eligible to titrate the cinacalcet dose at monthly titration visits (**beginning at week 4**) to a maximum dose of 2.5 mg/kg/day based on the subject's dry weight at **Study Day 1**, not to exceed a dose of 180 mg/day.

### 3.1.2 Subjects From Study 20110100

Eligible subjects will complete the End of Study visit or early termination visit for Study 20110100 and continue or restart cinacalcet treatment in this study on Study Day 1 depending on their cinacalcet treatment status at the time of enrollment, dry weight at the time of enrollment in 20140159 study and age at the time of enrollment in the 20110100 study. Subjects completing the 26-week treatment period in Study 20110100 will be screened during the safety follow-up period in Study 20110100; if eligible, these subjects will begin procedures in Study 20140159 at the Study 20110100 week 26 End of Study visit (Study Day 1 in 20140159 will be the same as EOS in Study 20110100). Subjects who reach Study 20110100 termination before week 26 will not complete the safety follow-up period in Study 20110100, beginning the 20140159 extension study at early termination visit. The early termination/EOS visit in study 20110100 and

---

Product: Cinacalcet HCl  
Statistical Analysis Plan: 20140159  
Date: 24 May 2016

Page 7 of 36

---

**Study Day 1 in Study 20140159 will be the same visit unless there is an administrative delay.**

**Eligible subjects will complete Study Day 1 assessments and confirm eligibility in IVR system before being dispensed IP on Study Day 1.**

**Eligible subjects will continue cinacalcet treatment on Study Day 1 based on their dry weight at the time of enrollment in 20140159 study if their iPTH is  $\geq$  150 pg/mL and cCa is  $\geq$  8.8 mg/dL (age < 2 years of age) or cCa is  $\geq$  8.4 mg/dL (age is  $\geq$  2 years of age) during screening in Study 20140159. If IP has been withheld or missed for > 14 days at the time of Study Day 1 of Study 20140159, the subject will resume dosing at the starting dose level based on dry weight at the time of enrollment once all restart criteria are met.**

**All subjects from 20110100 will be eligible to titrate the cinacalcet dose at monthly titration visits (beginning at week 4) to a maximum dose of 2.5 mg/kg/day based on the subject's dry weight at Study Day 1 in Study 20140159, not to exceed a dose of 60 mg/day.**

Cinacalcet dosing will follow the dose titration, dose withhold, and restarting rules defined in protocol Section 6.2.3.

### **3.2 Sample Size**

This is an extension study **for subjects from Study 20130356 and Study 20110100**. The sample size of approximately 48 for the parent study **20130356 and 30 for the parent Study 20110100** will result in a **planned** sample size of **78** subjects in **Study 20140159**.

### **4. Study Endpoints**

#### **Primary Endpoint:**

Incidence of treatment emergent adverse events of interest

#### **Secondary Endpoints:**

##### **20140159studyonly(forinterimandfinalanalyses)**

Achievement of  $\geq$ 30% reduction from baseline to mean iPTH during weeks 11 and 15 (SOC arm of Study 20130356 only)

Achievement of  $\geq$ 30% reduction from baseline to mean iPTH during weeks 23 and 28 (SOC arm of Study 20130356 only)

Percent change from baseline to mean iPTH during weeks 23 and 28 (SOC arm of Study 20130356 only)

**Change in corrected total serum calcium from baseline to mean value during week 23 and 28**

**Change in serum phosphorus from baseline to mean value during week 23 and 28**

**Achievement of a mean iPTH value  $\leq 300$  pg/mL during week 23 and 28**

Serum cCa values at **baseline**, week 11, and week 28

Serum phosphorus values at **baseline**, week 11, and week 28

**Combined20130356,20110100and20140159studies(forfinalanalysisonly)**

**Achievement of  $\geq 30\%$  reduction from day 1 of cinacalcet treatment to mean iPTH during weeks 11 and 15**

**Achievement of  $\geq 30\%$  reduction from day 1 of cinacalcet treatment to mean iPTH during weeks 23 and 28**

**Percent change in iPTH over time from day 1 of cinacalcet treatment**

**Change in serum cCa over time from day 1 of cinacalcet treatment**

**Change in serum phosphorus over time from day 1 of cinacalcet treatment**

**Exploratory Endpoint**

**20140159studyonly(forfinalanalysisonly)**

Growth velocity from **baseline** to EOS

Change in Tanner stage from **baseline** to EOS

**Combined20130356,20110100and20140159Studies(forfinalanalysisonly)**

**Growth velocity from day 1 of cinacalcet treatment to EOS**

**Change in Tanner stage from day 1 of cinacalcet treatment to EOS**

**Safety Endpoints:**

Nature, frequency, and severity of all adverse events

Blood pressure, heart rate, and changes in laboratory parameters, including clinical chemistry and hematology

**5. Hypotheses and/or Estimations**

There is no formal statistical testing for this study. The proportions of subjects with treatment emergent adverse events of interest will be estimated.

**6. Definitions**

**6.1 Study Periods**

**Screening**

The screening period begins when the informed consent, and assent if applicable, is signed and concludes when the subject is either enrolled into the trial or screen failed.

---

Product: Cinacalcet HCl  
Statistical Analysis Plan: 20140159  
Date: 24 May 2016

Page 9 of 36

---

The informed consent can be signed up to **7 days ( $\pm$  3 days)** prior to Study Day 1 of Study 20140159.

For subjects who do not meet the eligibility criteria in Section 4 of the protocol, re-screening will not be considered in this study.

**End of dose titration phase**

The end of dose titration phase is Week 24 of Study 20140159.

**Time on study**

If the subject has ended study, time on study (in days) is defined as: time on study = end of study date – study Day 1 +1.

Otherwise, time on study (in days) = data cutoff day – study Day 1 +1, which is applicable for interim analysis only.

**Time of follow-up (in days: use for follow-up adjusted AE for the final analysis)**

End of study date – Day 1 of cinacalcet treatment +1

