## 7.3.10 Adverse Events

Adverse events will be collected in the eCRF for each subject at all study visits. Targeted questions regarding hypocalcemia, seizures and infections will be asked and data will be entered into the eCRF at each study visit.

All clinically significant (according to the investigator's judgment), laboratory abnormalities will be reported as adverse events. In assessing clinical significance of a low serum calcium value, the investigator should consider factors such as presence of clinical symptoms associated with hypocalcaemia, dose adjustment of cinacalcet or concomitant medications (eg, vitamin D, phosphate binders). In addition, the investigator should indicate on the eCRF whether hypocalcemia was symptomatic, and if so provide the accompanying symptoms.

Serious adverse events that occur in a subject from the date of the first dose through 30 days after the last dose of IP will be recorded in the adverse event eCRF. All adverse events that occur from the date of the first dose through 30 days after the last dose of IP will be recorded in the adverse event eCRF. Refer to Section 9 for additional information.

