# 10.4.2 Primary Endpoint

The analysis of the primary endpoint will be based on the Safety Analysis Set. The primary analysis of the primary endpoint is subject incidence of events of interest (EOI;

CONFIDENTIAL

# Page 62 of 79

AMGEN

Page 63 of 79

eg, hypocalcemia, convulsions, hypotension, worsening of heart failure, hypersensitivity, ischemic heart disease, QT prolongation/ventricular tachyarrhythmias, fracture, acute pancreatitis, drug-related hepatic disorders, nervous system disorders [excluding seizures], neoplastic events, and infection) for data in the 20140159 study only. The secondary analysis of the primary endpoint is the incidence of events of interest adjusted by the amount of safety follow-up time for combined data from parent studies and data from the 20140159 study. The 95% confidence intervals (CI) of the overall incidence rates will be reported.

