#### 10.4.4 Safety Endpoints

The safety analysis will be based on the safety analysis set. All safety endpoints in 20140159 study only and combined with their parent studies will be summarized by treatment group in the parent studies and overall.

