**Study Day 1**

The date that the initial dose of IP is administered in Study 20140159. For subjects who didn't take any IP throughout the study, leave as missing.

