**Day 1 of cinacalcet treatment (combined studies 20130356, 20110100 and 20140159)**

The date that the initial dose of cinacalcet treatment is administered in studies 20130356, 20110100 or 20140159.

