#### **10.5 Analysis of Primary Endpoint**

The primary endpoint is incidence of treatment emergent adverse events of interest as defined in **Section 6.4**. The analysis will be based on Safety Analysis Set. Subject incidence of EOIs will be summarized by EOI category and **preferred term for data in Study 20140159 only for both the interim and final analyses. The 95% confidence intervals (CI) of the overall subject incidence rates will be reported.**

**The secondary analysis of the primary endpoint is follow-up time adjusted incidence of EOIs for combined data from parent studies and data from the 20140159 study for the final analysis.**

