**Combined20130356, 20140159and20110100studies**

**Subject follow-up time adjusted incidence of all treatment-emergent AEs and EOIs, defined for studies 20130356, 20140159 and 20110100 combined in section 6.4, will also be tabulated by preferred term in descending order of follow-up time adjusted incidence rates for all subjects.**

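### The combined follow-up-adjusted event rates use an unbroken span from first cinacalcet dose to end of study, so between-study days without required adverse event collection tend to lower the rate for delayed subjects

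*SAP*

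**What the plan says.** Protocol 10.4.2 makes the secondary analysis of the primary endpoint an incidence "adjusted by the amount of safety follow-up time for combined data from parent studies and data from the 20140159 study". SAP 10.5 carries this forward as "follow-up time adjusted incidence of EOIs for combined data from parent studies and data from the 20140159 study for the final analysis", and SAP 10.7.1 (combined studies) adds "Subject follow-up time adjusted incidence of all treatment-emergent AEs and EOIs".

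SAP 6.1 defines the follow-up time for these analyses as "End of study date – Day 1 of cinacalcet treatment +1". SAP 6.2 gives the start as "The date that the initial dose of cinacalcet treatment is administered in studies 20130356, 20110100 or 20140159". For the 20130356 cinacalcet arm and all 20110100 subjects, that date lies in the parent study. Nothing in the SAP subtracts time between studies. Study Day 1 of the extension is "The date that the initial dose of IP is administered in Study 20140159".

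On event collection, Protocol 7.3.10 says: "All adverse events that occur from the date of the first dose through 30 days after the last dose of IP" go on the adverse event form. Protocol 9.2.1 and 9.2.2 start their windows at the same point. The parent safety follow-up is waived for 20130356 rollovers (Protocol 2.5.1) and for 20110100 subjects who enter when that study is terminated (2.5.2).

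Same-visit entry is the default, but later first dosing is provided for:
- an administrative delay (Protocol 3.1.1, 3.1.2);
- more than 14 days since the last parent visit (4.1.1, 4.1.2, Table 4 footnote 2);
- enrolment while the dose is withheld (Section 4).

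SAP 10.6.2 has a sensitivity analysis for interruptions of more than 14 days between the parent end-of-treatment visit and Study Day 1, but only for iPTH.

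**The concern.** A follow-up-adjusted rate needs a denominator that counts time during which an event would have been recorded. The SAP counts calendar time from first dose to end of study. The two agree when a subject moves from one study to the other at a single visit and is dosed that day. They part when a parent-cinacalcet subject has days after parent collection ended and before the first 20140159 dose. Those days add to the denominator, while the plan contains no requirement that would reliably add their events to the numerator.

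The direction is therefore towards a lower rate, in a study whose primary objective is to characterise safety. The analysis concerned is the planned secondary analysis of the primary endpoint, and the protocol's description of it is not met for delayed subjects.

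**Working it through.** The plan states no rate, person-time or gap length, so there is no figure to reproduce. The check is a person-time calculation at the planned numbers.

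**Inputs from the documents**
- 20130356: about 48 subjects randomised 1:1, so 24 cinacalcet and 24 standard of care; 20 weeks of treatment (Protocol 2.5.1).
- 20110100: 30 subjects (SAP 3.2); 24 weeks of treatment plus 2 weeks of follow-up (Protocol 2.5.2). 48 + 30 = 78, which agrees with SAP 3.2.
- 20140159: 32 weeks (Protocol 3.5.1).

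**Assumptions**
- All planned subjects enter and complete.
- The rate is a count divided by total follow-up time. The SAP gives no formula.
- 10% or 25% of the 54 parent-cinacalcet subjects are delayed (n = 5.4 or 13.5), by G = 30 or 90 days.
- The parent study collected events for P = 0 or 30 days after its last visit.
- No events are captured on the remaining gap days.
- The +1 day is ignored.

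**Days under collection with no gap**
- 20130356 cinacalcet: 20 + 32 weeks = 364 days; 24 × 364 = 8,736.
- 20110100: 26 + 32 weeks = 406 days; 30 × 406 = 12,180.
- Former standard of care: 32 weeks = 224 days; 24 × 224 = 5,376.
- Total: 26,292.

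**Formula.** Rate under SAP 6.1 ÷ rate over observed days = (26,292 + n × P) ÷ (26,292 + n × G), with P no larger than G.

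| Share delayed | G (days) | P = 0 | P = 30 |
|---|---|---|---|
| 10% | 30 | 26,292/26,454 = 0.994 (0.6% low) | 1.000 (0%) |
| 10% | 90 | 26,292/26,778 = 0.982 (1.8% low) | 26,454/26,778 = 0.988 (1.2% low) |
| 25% | 30 | 26,292/26,697 = 0.985 (1.5% low) | 1.000 (0%) |
| 25% | 90 | 26,292/27,507 = 0.956 (4.4% low) | 26,697/27,507 = 0.971 (2.9% low) |

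**One 20130356 cinacalcet subject with a 90-day gap.** The contribution to the denominator is 364 + 90 = 454 days. Observed share: 364/454 = 0.802 (19.8% low), or 394/454 = 0.868 (13.2% low) with 30 days of parent collection.

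**Subjects with no effect.** For former standard-of-care subjects, Day 1 of cinacalcet treatment is Study Day 1, so G = 0. For same-visit rollovers dosed that day, G = 0 as well.

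**The case against.** The strongest reply is that gap events may be recorded after all. In Table 4 the adverse event and serious adverse event rows carry footnote 2, which calls for procedures at the 20140159 screening visit when more than 14 days have passed since the last parent visit, for subjects affected by study termination. Protocol 7.3.10 also says adverse events are collected at all study visits, which would include visits by a subject enrolled with the dose withheld. SAP 9.3.2.1 refers to a form question on whether an event began before the first dose. The combined treatment-emergent definition in SAP 6.4 would count such events, because it runs from first cinacalcet dose without a break. The parent collection windows are not supplied, and a waived follow-up visit does not prove that parent collection stopped.

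This stands to the extent that a reader should not infer that gap days cannot yield recorded events. It does not remove the point. The stated window in 7.3.10 and 9.2.1 still begins at the first 20140159 dose. The footnote covers only some delayed subjects, and the screening cell on those rows appears empty in the text available. No passage requires complete collection over the gap.

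The scenarios are also not anchored in the documents. Entry is within 7 days unless there is an administrative delay (Protocol 2.5.1, 2.5.2). The dosing rules for more than one month count from the last dose, so a subject whose dose was withheld could meet them while still observed in the parent study. That is fair, and it is why the shares and gap lengths are labelled as assumptions.

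The effect is also small beside sampling error. With 30 events (an assumption), an exact Poisson 95% interval runs from about 33% below to 43% above the estimate. That limits the importance of the point, but it is no reason to keep a denominator that differs from the protocol's.

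A reader might further infer that comparisons between parent groups are distorted, since only parent-cinacalcet subjects can be affected and Protocol 10.4.4 has safety endpoints "combined with their parent studies will be summarized by treatment group in the parent studies and overall". SAP 10.7.1, however, tabulates the adjusted rates for all subjects together, so a by-group display of these rates is uncertain. The groups also differ in age and in length of follow-up.

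**Conclusion.** The point holds in a limited form. The SAP's denominator is not the amount of safety follow-up time for parent-cinacalcet subjects with an uncollected gap, and the resulting rate tends to be too low. Under the assumed shares and delays the pooled rate is about 0.6% to 4.4% low. It is less if the parent study collected events after its last visit or if gap events are captured at 20140159 screening. The documents do not support a claim that the reported rates will be materially biased, because they give neither the number nor the length of gaps. The analysis is descriptive, and the primary analysis, subject incidence in 20140159 alone, is unaffected. The correction is worth making before the final analysis because it is cheap and removes a departure from the protocol's own description.

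**What to change.** In SAP 6.1, define follow-up time for the combined adjusted rates as the sum of two periods:
- (a) Day 1 of cinacalcet treatment to the earlier of the end of parent-study adverse event collection and the day before 20140159 Study Day 1;
- (b) 20140159 Study Day 1 to the 20140159 end of study date.

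Former standard-of-care subjects have only (b), and no day is counted twice. State the parent collection end date used for each parent study. Keeping the SAP's present end point leaves subjects without a gap unchanged. For a same-visit 20130356 cinacalcet rollover with a 30-day parent window, min(170, 140) + 224 = 364 days, as now. With a 90-day gap and no parent cover, the result is 140 + 224 = 364 instead of 454. Ending (b) at the close of adverse event collection instead would alter the result for subjects who stop treatment but stay on study, so that should not be done under this change.

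In SAP 6.4, count in the combined adjusted rates only events with onset within (a) or (b), so that numerator and denominator match. List any recorded gap events separately, and report the number and length of gaps.

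The cost is a short SAP amendment and some programming for the final analysis. No new data are collected, because the combined analysis already draws on the parent-study data.
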